STUDY PROTOCOL

Title: The Effect of Using Crochet Octopus in Reducing The Pain Developed During The Process of Heel Lance In Neonates: A Randomized Controlled Study

NCT number: 04560374

Document date: May 1, 2020

Objectives: The main objective of this study was to determine the effect of using a crochet octopus to reduce acute pain that develops during a heel lance in neonates.

Design: This study used a randomized controlled design.

Methods:

Participants: Neonates born between May 1, 2020, and August 15, 2020, were included in the study. The study was conducted at a well-child unit in a research and training hospital with healthy, term neonates. The neonates were not hospitalized during the research. All blood samples for the Guthrie test were routinely taken at the well-child unit in this hospital.

Measurements: Descriptive data of participant neonates were documented in the neonatal identification form using hospital records. The pain score measured with Neonatal Infant Pain Scale.

Intervention: The crochet octopus was delivered to the hands of the neonates in the experimental group 10 min before the heel lance process occurred, and the neonates were in contact with the crochet octopus for up to 10 min after the procedure (Figure 3). In this procedure, the neonates were dressed. The procedure was carried out under a radiant heater in baby mode, and neonates were placed in a supine position. A pulse oximeter device was used

to monitor oxygen saturation and heart rate. The device probe was attached to the neonates' wrists during the time under the radiant heater. The respiratory rate was counted by one researcher for 1 min. The body temperature was measured by researcher with an infrared thermometer. The observation form was completed before the procedure began (0th min). No intervention was performed beforehand to better draw the heel blood, and the blood was drawn from the left heel for each neonate because of the researcher's holding position. A fine lancet was used for heel lancing; before the procedure, the heel was wiped with 70% isopropyl alcohol wipes in a circular motion and then wiped with dry cotton. Blood was drawn from the heel while the neonate was on the mother's laps. The observation form was completed again during the procedure and after the procedure (at 2nd and 10th min).

The total data collection time took an average of 20 min, and the entire process was recorded on video. After the process, researcher performed the heel lance procedure with video recording. After the procedure was completed, video recordings were assessed by two observers—a neonatal nurse specialist and researcher—together to eliminate bias. Neonatal durations of crying and NIPS scores were calculated at 0 min (before the procedure) and at 2nd and 10th min after the process, and the scores were recorded on the data collection form. During the procedure, neonates remained with the mothers. Neonates who cried before the procedure were held by mothers until they calmed down; approximately 15 min later, they could be included in the study.

Before collecting the data, 50 crochet octopus were crocheted by three researchers according to the standards noted in the Methods' Instruments section. A new crochet octopus was used for each neonates during the heel lance procedure; the octopus was then washed in a washing machine with an organic detergent for neonates in 60°C (hot) water.

The control group of neonates underwent the heel lance process without a crochet octopus.

Ethical Considerations: Ethical approval was obtained from the Clinical Researchers Ethical Committee of Giresun University (Approval No. 06.02.2020/20). Institutional permission was obtained from the Public Hospitals Association of Giresun. In addition, parents of the neonates were asked for written informed consent forms for the data collection, procedure, and video recording.

Statistical Analysis Plan

The Number Cruncher Statistical System (NCSS 2007; Kaysville, UT, USA) was used for statistical analysis. Descriptive statistical methods (average, standard deviation, median, quartiles, frequency, rate, minimum/maximum) were used to assess relevant data. Normal distribution characteristics of the study parameters were examined with the Kolmogorov-Smirnov test. Heart rate, oxygen saturation, and body temperature had normal distributions, but respiratory rate, duration of crying, and NIPS pain scores did not have normal distributions. The independent *t*-test was used for the cross-group comparison of variables with normal distributions, and the Mann-Whitney *U* test was used for those without normal distributions. Cohen's kappa coefficient was calculated for the interrater reliability of observers. Significance was assessed in the range of 95% reliability.

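### Could the rule for infants who cry beforehand act after allocation and let entry or maternal holding differ by arm?

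*Combined protocol and SAP*

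**What the plan says.** All the relevant text is in the Intervention part of the protocol's Methods.

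- **Crying rule:** "Neonates who cried before the procedure were held by mothers until they calmed down; approximately 15 min later, they could be included" in the study.
- **Exposure:** "The crochet octopus was delivered to the hands of the neonates in the experimental group 10 min before the heel lance process occurred", and "neonates were in contact with the crochet octopus for up to 10 min after the procedure". The control group has the lance without the octopus, and no matching lead-in period is described for it.
- **Outcome timing:** "Neonatal durations of crying and NIPS scores were calculated at 0 min (before the procedure") and again at 2 and 10 min.
- **Duration:** "The total data collection time took an average of 20 min", and sessions were filmed throughout.
- **Setting:** "The procedure was carried out under a radiant heater in baby mode, and neonates were placed in a supine position"; also "Blood was drawn from the heel while the neonate was on the" mother's lap, and "During the procedure, neonates remained with the mothers".

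Randomisation appears only as the name of the design, with no timing, sequence or concealment. The Statistical Analysis Plan compares the groups with unadjusted t and Mann-Whitney tests. It does not mention infants who were held, deferred or not entered.

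**The concern.** Crying is both a condition for taking part and a measured outcome. The rule and the 0-min measurement are each tied to the time before the *procedure*. If that word means the lance, this time includes the 10 min in which only the experimental arm has the octopus. An infant could then be allocated, given the octopus, cry or not cry partly because of it, and be held or left out as a result.

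Two things would follow. Maternal holding could be more common in one arm. Entry could also depend on a response to treatment, because *could be included* can be read as optional, the octopus is visible, and no blinding is described for whoever applies the rule. Either would weaken the protection that randomisation gives, and a two-group test without adjustment would carry the distortion into the 0-min values and possibly the later ones.

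**Working it through.** The documents give no sample size, effect size or counts for this point, so there is no stated figure to reproduce. The check is the order of steps, plus arithmetic on the stated minutes.

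**1. The three possible orders**

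| Order | Consequence |
|---|---|
| Crying check, then randomisation, then octopus | Crying cannot depend on the arm. Bias is zero. |
| Randomisation, then crying check, then octopus | The octopus cannot yet have changed crying, so holding is balanced on average. Only selective non-entry by someone who knows the allocation could matter. |
| Randomisation, then octopus, then crying check | Both holding and entry could depend on the arm. |

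The full concern needs the third order.

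**2. Does the third order fit the schedule?** Inputs: octopus placed 10 min before the lance, contact for up to 10 min after, a wait of about 15 min, average session 20 min.

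- Without a hold: 10 + 10 = 20 min, equal to the stated average.
- With a hold inside the session: 10 + 15 + 10 = 35 min for that infant.
- If an experimental infant cries *t* min after placement and then waits 15 min, contact before the lance is at least *t* + 15, so at least 15 min. The stated contact is 10 min. The third order works only if the octopus is taken away and the clock restarted, and nothing in the text describes that.

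**3. What the average can show.** If a share *f* of infants were held inside the session, the mean would be 20 + 15*f*:

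- *f* = 0.05: 20 + 0.75 = 20.75 min
- *f* = 0.20: 20 + 3.0 = 23.0 min

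Frequent holding inside the session fits poorly with 20 min, while rare holding could not be told apart from it. This is weak evidence: the average is probably rounded, the time taken by the lance is left out, and contact afterwards is only *up to* 10 min.

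**4. What *procedure* means.** The 0-min measurement follows the start of exposure only if the word means the lance. The protocol uses it loosely. In one place it covers being placed supine under the heater, although the blood itself is drawn on the mother's lap. It can therefore mean the whole session, octopus included, and the shared phrase does not show that the rule acts after allocation.

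**5. Size.** Bias from holding = (difference in share held) × (effect of holding on NIPS). Neither factor is in the documents. If one assumes 0 to 10 percentage points and 1 to 2 NIPS points, the product runs from 0 to 0.10 × 2 = 0.2 point, towards no effect if control infants are held more. Both ranges are assumptions, so this illustrates the scale and is not an estimate.

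**The case for a change.** The best case for acting is that randomisation protects the comparison only if no selection follows it, and a reader cannot verify that from this text. An average session time does not fix the order of steps. Even a hold that ended before the session clock started would not place randomisation, since an infant might be allocated, then held, then given the octopus. No analysis set is defined, and nothing says what becomes of an infant who never calms. One sentence would settle the matter.

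Much of this stands as a description of what is missing. It does not show that the plan as written leads to a faulty comparison. Allocation followed by a hold before the octopus leaves holding unrelated to the toy; what is left is discretionary non-entry, which the text does not suggest. *Could* reads more easily as *became eligible* than as licence to drop an allocated infant. The silence on the timing of randomisation is part of a wider silence on its method, and the crying rule is only one consequence of that.

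Rewording would also gain little. The protocol is written in the past tense, and the Statistical Analysis Plan already reports which variables were normally distributed. A new rule or a new item on the form would not alter how infants were handled if data collection has ended, and choosing when infants are randomised or held goes beyond reconciling the text.

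**Conclusion.** No change to the plan is called for. The order of crying check, randomisation and octopus placement is unstated, but the natural reading is deferral before entry. This rests on taking inclusion in the study to mean enrolment and on the 10-min lead-in being kept as described. The text does not positively exclude use of the rule after allocation, and if that occurred its effect cannot be sized from the documents.

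Analysts can fill the gap sensibly when reporting: state the order used, give by arm any infants held, deferred or not entered after allocation (the video may help for holding within the session), and confirm that all randomised infants were analysed as assigned.

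The heater-and-supine and mother's-lap statements are a separate matter of description and must be reconciled. They may describe successive phases. Neither is limited to one arm, so they show no difference between the groups and do not bear on this point.

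### The SAP makes no use of each infant's pre-procedure vital signs; adjusting for a reading taken before the octopus is handed over could gain precision, but the plan does not say whether the 0-min reading is one

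*Combined protocol and SAP*

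**What the plan says.** **Measurement (Methods, Intervention).** A pulse oximeter is used "to monitor oxygen saturation and heart rate". For the other two vital signs: "The respiratory rate was counted by one researcher for 1 min" and "The body temperature was measured by researcher with an infrared thermometer". The text then turns to the observation form: "The observation form was completed before the procedure began (0th min)" and, later, "The observation form was completed again during the procedure and after the procedure (at 2nd and 10th min)". The form's contents are not listed.

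**Start of the intervention (same section).** The octopus "was delivered to the hands of the neonates in the experimental group 10 min before the heel lance process occurred". The text does not say whether the 0-min form comes before or after this handover.

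**Analysis (Statistical Analysis Plan).** The variables are sorted by distribution: "Heart rate, oxygen saturation, and body temperature had normal distributions, but respiratory rate, duration of crying, and NIPS pain scores did not". The t-test "was used for the cross-group comparison of variables with normal distributions", and Mann-Whitney U serves the rest. No covariate adjustment, change score, paired test or repeated-measures model is named. The time point and scale (level or change) of each comparison are not stated.

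**The concern.** The objective concerns pain that arises during the lance, which is a response from each infant's own starting level. Resting heart rate and respiratory rate can be expected to differ between infants. A two-sample test on later levels counts that stable difference as noise, although a reading that could remove part of it may already have been taken.

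Two things are at stake. The first is precision: the physiological comparisons may be less sensitive than the collected data allow. The second is chance imbalance: if the arms happen to differ at rest, part of that difference carries into the later comparison and the named tests do not correct for it.

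**Working it through.** The plan states no sample size, power, SD or correlation, so it has no figure to reproduce. The check asks how much adjustment would gain if a true baseline exists, and what it would do if the 0-min value is not one.

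**Inputs**
- Arm size: not stated. The Intervention text says that 50 octopuses were made and a new one was used for each infant. I assume 50 per arm, with 30 as a lower case, and 1:1 allocation.
- Alpha: 5%, from the SAP's 95% level; two-sided is assumed.
- Correlation r between baseline and later value: not stated; 0.3, 0.5 and 0.7 assumed.
- True effect at the later time: 0.5 SD, assumed.

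**1. Variance.** ANCOVA variance ÷ unadjusted variance = 1 − r². The equivalent gain in infants is 1/(1 − r²). Power and the detectable difference (80% power) come from the noncentral t with SD = √(1 − r²).

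| r | 1 − r² | Variance cut | Equivalent infants | Detectable difference, 50/arm | Power for 0.5 SD, 50/arm | Power for 0.5 SD, 30/arm |
|---|---|---|---|---|---|---|
| unadjusted | 1.00 | – | 1.00 | 0.566 SD | 69.7% | 47.8% |
| 0.3 | 0.91 | 9% | 1.10 | 0.540 SD | 73.7% | 51.4% |
| 0.5 | 0.75 | 25% | 1.33 | 0.490 SD | 81.5% | 59.4% |
| 0.7 | 0.51 | 49% | 1.96 | 0.404 SD | 93.4% | 76.0% |

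At r = 0.1 and 0.2 the variance cut is only 1% and 4%. These are normal-theory figures. They apply to heart rate, oxygen saturation and temperature, and are only a guide for respiratory rate.

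**2. Chance imbalance.** The baseline difference between arms has standard error √(2/50) = 0.20 SD. The unadjusted comparison moves by r × imbalance: for a 0.20 SD imbalance, 0.06, 0.10 and 0.14 SD. Given a 2-standard-error imbalance, the unadjusted z-statistic has mean 2r and SD √(1 − r²) under the null. The conditional false-positive rate is then 8.1%, 13.4% and 21.6% at the three correlations. An imbalance that large or larger occurs by chance in about 5% of trials per variable. Over all randomizations the rate is still 5%.

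**3. If the 0-min value is read with the octopus already in hand.** Suppose the octopus has shifted the 0-min value by g = 0.25 SD. ANCOVA then estimates 0.5 − r × g = 0.425, 0.375 and 0.325 SD instead of the total effect of 0.50. In 4,000 simulated trials per setting at 50 per arm, the ANCOVA means were 0.426, 0.375 and 0.324. Power was 59%, 56% and 61%, against 70%, 69% and 69% unadjusted. With g = 0.5 SD the estimates fall to 0.35, 0.25 and 0.15.

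**4. Change scores.** Change-score variance ÷ unadjusted variance = 2(1 − r) = 1.4, 1.0 and 0.6. Below r = 0.5 a change score is less precise than ignoring baseline.

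**The case against.** The strongest objection is that the plan may contain no usable baseline. The octopus is in hand from 10 min before the lance. The later readings are numbered as 2 and 10 min after the process, which suggests that 0 min lies close to the lance. The average collection time of 20 min also fits 10 min before plus 10 min after. On that reading the SAP is right not to adjust for the 0-min value, and a difference at 0 min could be a treatment effect rather than chance. This stands, and it is why the timing must be settled first. It does not dispose of the point: the documents do not fix the order, and the SAP should say what the 0-min value is for.

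Three other objections hold in part:
- Repeated vital signs are inferred. Only crying and NIPS have explicit 0-, 2- and 10-min values. The inference is natural, because the vital signs are described immediately before the form.
- The correlation is unknown and need not be the same for all four variables. Infants lie supine under a heater but are bled on the mother's lap, so conditions may differ between readings and r may be low.
- The variables concerned are not the pain score that serves the main objective.

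A reader might infer more than the text supports. It does not say that arms are compared on raw later values; the SAP is silent on time point and scale. Nor does it follow that the results are biased or the error rate inflated, since randomization protects both on average, or that an imbalance passes into the result in full, since only r times it does. Nor can NIPS and crying be set aside on the ground that they start near zero: the documents give no 0-min levels, and describe calming only for infants who cried beforehand.

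**Conclusion.** The point holds as a conditional efficiency weakness. The SAP names only unadjusted between-arm tests and assigns no role to the pre-procedure reading. Those tests are valid. The loss lies in precision and in conditional balance, for heart rate, oxygen saturation, temperature and respiratory rate.

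Its size depends on an unstated correlation: modest at 0.3, worthwhile from 0.5, negligible at 0.1 to 0.2. The power figures also assume 50 infants per arm, equal allocation and a 0.5 SD effect. All of the gain requires a reading taken before handover; with a later one, adjustment can do harm. The figures say nothing about NIPS or crying, where the SAP leaves the role of the 0-min value equally open.

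**What to change.** 1. State in the Intervention section whether the 0-min form is completed before the octopus is handed over, and which vital signs the form records at each time.
2. Define the covariate as a reading taken before handover, with the same oximeter, respiratory count and thermometer, and at the matching time in the control arm.
3. In the SAP, compare later heart rate, oxygen saturation and temperature by ANCOVA with arm and that value, or by one mixed model per variable with arm, time, arm-by-time and that value. Use a rank-based or transformed ANCOVA for respiratory rate. State the time points. Report adjusted differences with 95% confidence intervals where the scale allows, and keep the unadjusted tests as sensitivity analyses.
4. If the only 0-min reading follows handover, analyse it as an outcome and do not adjust for it. For infants already studied without an earlier reading, the unadjusted comparison stays.
5. Do not substitute simple change scores.

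The cost is SAP wording and one regression per variable. If the 0-min form follows handover, add one brief extra set of readings per infant. No extra infants are needed.

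### Cohen's kappa is the only reliability measure named, with no weights, variable or time point; on its natural unweighted reading it suits neither the NIPS total nor crying duration

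*Combined protocol and SAP*

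**What the plan says.** Reliability is dealt with in a single sentence of the Statistical Analysis Plan: "Cohen's kappa coefficient was calculated for the interrater reliability of observers". No weighting scheme, variable, time point, pooling rule or acceptance threshold follows, and no second measure is named.

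The Intervention text under Methods says what was derived from the recordings: "Neonatal durations of crying and NIPS scores were calculated at 0 min (before the procedure) and at 2nd and 10th min after the process". The Measurements paragraph names the instrument ("The pain score measured with Neonatal Infant Pain Scale") but gives no score range. The Statistical Analysis Plan treats both video outcomes as quantities to be ranked: it reports that "respiratory rate, duration of crying, and NIPS pain scores did not have normal distributions" and assigns such variables to the Mann-Whitney U test.

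Two more statements in the Intervention text bear on the coefficient. On the state at 0 min: "Neonates who cried before the procedure were held by mothers until they calmed down". On how the rating was done: "video recordings were assessed by two observers—a neonatal nurse specialist and researcher—together to eliminate bias".

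**The concern.** Cohen's kappa without weights is built for unordered categories. It asks only whether two ratings are identical. The plan uses the ordering of NIPS and crying time when it compares the groups, yet for reliability it names a coefficient that, unless weights are stated, discards that ordering.

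There are three consequences to check:

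- **NIPS total.** An unweighted kappa cannot tell observers who differ by one point from observers who differ by several.
- **Crying duration.** Two careful timings in seconds are rarely identical, so a kappa would look poor whatever the real agreement. If kappa was not used for crying time, no reliability measure is stated for that outcome at all.
- **Time points.** One coefficient over 0, 2 and 10 min would mix calm records with records taken after the lance, and the mix would influence its value.

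This kappa is the only evidence the plan offers that its pain score is reproducible.

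**Working it through.** The documents report no kappa value and no agreement table, so there is no figure to reproduce. The figures below rest on assumed data. They show direction and range, not this trial's values.

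**Formula.** Kappa = 1 − Σ(d × observed) / Σ(d × expected), where d is the penalty for a pair of ratings (i, j). Unweighted: d = 0 if equal, 1 otherwise. Linear: d = |i − j|. Quadratic: d = (i − j)².

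**Step 1: NIPS total, differences of one point only.** Assumptions: 8 levels (0-7); observer A uniform over 1 to 6; observer B equal to A with probability 0.70, otherwise one point higher or lower with probability 0.15 each.

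- Unweighted. B falls outside 1-6 with probability 2 × (1/6) × 0.15 = 0.05. Chance agreement = 0.95/6 = 0.158. Kappa = (0.70 − 0.158)/(1 − 0.158) = **0.64**.
- Linear. Mean observed difference = 0.30. Mean difference expected by chance = 2 × (0.025 × 3.5 + 0.1417 × 2.5 + 0.1667 × 1.833 + 0.1667 × 1.5) = 1.994. Kappa = 1 − 0.30/1.994 = **0.85**.
- Quadratic. Mean observed squared difference = 0.30. Expected = variance of A + variance of B = 2.917 + (2.917 + 0.30) = 6.133. Kappa = 1 − 0.30/6.133 = **0.95**.

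With 40% of pairs one point apart, the three values are 0.53, 0.80 and 0.94.

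**Step 2: same exact agreement, different severity.** A second assumed score distribution on 0-7, with exact agreement held at 70%:

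| Non-identical pairs | Unweighted | Linear | Quadratic |
|---|---|---|---|
| all 1 point apart | 0.64 | 0.85 | 0.95 |
| all 3 or more points apart | 0.65 | 0.47 | 0.35 |

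The unweighted value hardly moves, although the second pair of observers is far worse.

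**Step 3: scale length.** The range is assumed, so step 1 was repeated at 30% with 6, 8 and 11 levels. Unweighted kappa is 0.61, 0.64 and 0.66; linear-weighted is 0.77, 0.85 and 0.90. The direction holds throughout, but the gap runs from 0.16 to 0.24, so its size depends on the scale.

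**Step 4: crying duration.** Simulated in whole seconds (lognormal, median 40 s, limited to 1-180 s), with independent timing error in each observer:

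| Error SD | Unweighted kappa | Between-observer correlation |
|---|---|---|
| 1 s | 0.26 | 0.999 |
| 2 s | 0.13 | 0.996 |
| 3 s | 0.08 | 0.990 |

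Gamma-distributed times with mean 30 s give the same kappas, with correlation at least 0.98.

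**Step 5: pooling 0 min.** Take the step 1 records as two thirds of the data and add one third at 0 min. If both observers score every 0-min record 0:

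- observed agreement = 1/3 + (2/3) × 0.70 = 0.80;
- chance agreement = (1/3) × (1/3 + (2/3) × 0.025) + (4/9) × 0.158 = 0.187;
- kappa = (0.80 − 0.187)/(1 − 0.187) = **0.75**, against 0.64 unpooled.

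If the observers sometimes split 0 against 1 at 0 min:

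| Agreement at 0 min | 100% | 90% | 80% | 70% | 60% |
|---|---|---|---|---|---|
| Pooled kappa | 0.75 | 0.72 | 0.68 | 0.64 | 0.60 |

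The rise is gone at 70% and reversed at 60%. It is also small if many post-lance records are themselves zero for both observers: with 40% such records, 0.77 becomes 0.80. Under other assumed distributions the break-even agreement at 0 min lay between about 0.71 and 0.92.

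**The case against.** The strongest reply is that the sentence is silent rather than wrong. It does not say unweighted, does not mention crying time, and does not say the times were pooled. Kappa on individual NIPS items or on a cut-off would fit the same words and could be suitable. This stands: a reader might infer that an unweighted kappa was applied to seconds of crying, or to all records together, but the text shows neither. Unweighted is still the natural reading when no weights are named. If crying time was left out, its reliability is simply not addressed.

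A reader might also infer that pooling must inflate the coefficient, because crying infants were calmed first. Step 5 does not support that: inflation needs high agreement at 0 min, which is plausible but not documented. Missing weights and pooling can also push in opposite directions, so no net bias is shown.

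Third, kappa plays no part in the Mann-Whitney comparison, and no threshold is set for it to fail. That stands too, and it limits the importance of the point.

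Finally, any agreement coefficient needs two separate scores per record. The observers are described as assessing the recordings together, so these may not exist. That question comes first, and the fix has to address it.

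**Conclusion.** The point holds in a limited form. The plan's only reliability measure is unspecified in weighting, variable and time. On its natural reading it is a poor choice for the NIPS total (0.64 unweighted against 0.85 linear and 0.95 quadratic, on an assumed 0-7 scale with 30% of pairs one point apart). It is unsuitable for crying duration (0.08 to 0.26 where the correlation is at least 0.98). Pooling 0 min could move it either way.

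These sizes rest on assumed score distributions, an assumed score range and assumed timing errors. They do not estimate this trial's kappa. Nor do they support an inference that the treatment result is biased: no group estimate or p-value depends on this coefficient. What is weakened is the evidence that the pain measure is reproducible. Minor priority.

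**What to change.** First state whether each observer recorded a separate score before any joint discussion. If so, replace the reliability sentence with wording such as:

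> Agreement is calculated from each observer's own score, recorded before any joint discussion, and is reported separately at 0, 2 and 10 min; 0 min is not pooled with the post-lance times. For the NIPS total, a weighted kappa is used, with weights fixed in advance. For crying duration, an absolute-agreement intraclass correlation and the mean between-observer difference are used. Each is given with a 95% confidence interval.

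The weights must be named beforehand because the choice matters (0.85 linear against 0.95 quadratic in step 1); either can be defended.

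If only a joint consensus score exists, no inter-rater coefficient can be claimed and the sentence should be removed, unless the recordings are scored again independently.

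Cost: where separate scores exist, one sentence and a few lines of output. Where they do not, a reliability claim costs a second rating of the videos. The downside is several coefficients instead of one.

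### The SAP does not say which post-lance NIPS time, or whether one or both, decides the pain objective; if either time counts, the two-sided error is above 5% and up to 9.75%.

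*Combined protocol and SAP*

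**What the plan says.** The Objectives section states a single main aim, that the octopus should serve "to reduce acute pain that develops during a heel lance in neonates". Measurements names one pain instrument: "The pain score measured with Neonatal Infant Pain Scale". The Intervention section gives the scoring times: "Neonatal durations of crying and NIPS scores were calculated at 0 min (before the procedure) and at 2nd and 10th min after the process". An earlier sentence in the same section concerns a different form: "The observation form was completed again during the procedure and after the procedure (at 2nd and 10th min").

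The Statistical Analysis Plan sorts the variables by distribution: "Heart rate, oxygen saturation, and body temperature had normal distributions, but respiratory rate, duration of crying, and NIPS pain scores did not" have them. NIPS therefore goes to a between-group Mann-Whitney test. The only decision rule is "Significance was assessed in the range of 95% reliability". The plan has no primary time point, success rule, testing order, repeated-measures model or multiplicity adjustment.

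Two dates bear on the remedy: "Document date: May 1, 2020" and "Neonates born between May 1, 2020, and August 15, 2020, were included in the study".

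**The concern.** NIPS is the only named pain measure, so the outcome for the main objective can be identified. What cannot be identified is the comparison that decides it. The 0-minute score precedes the lance and cannot show an effect on lance pain. That leaves the 2-minute and 10-minute comparisons, which have equal standing. The SAP does not list the times tested, but the natural reading is that each scored time is compared between groups at the same level.

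Nothing in this document prevents the pain claim from resting on whichever of the two is significant. Used that way, the 5% attached to each test is not the error rate of the claim.

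The document also cannot show that a time was chosen beforehand. It carries the date of the first day of the birth window, yet its SAP reports the distributions that the study variables turned out to have. At least that part was written after data were available.

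**Working it through.** **Inputs**

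- Level per test: 5%, from the 95% rule in the Statistical Analysis Plan.
- Sidedness: not stated; two-sided assumed.
- Post-lance NIPS tests: two (2 and 10 minutes), from the Intervention section.
- Correlation r between the two test statistics: not given. The same infants are scored at both times, so it is probably positive; 0 to 0.99 is shown.
- Sample size: not given, and not needed for the main calculation.

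**The plan's own figure.** One two-sided test with critical value 1.96 has error 0.0500, which matches the 95% rule.

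**Formulas.** Let Z1 and Z2 be the two test statistics, bivariate normal with correlation r, and let the octopus have no effect.

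- Either time significant: 1 − P(|Z1| < 1.96 and |Z2| < 1.96). At r = 0 this is 1 − 0.95² = 0.0975.
- Either time significant in the octopus's favour: 1 − P(Z1 < 1.96 and Z2 < 1.96). At r = 0 this is 1 − 0.975² = 0.0494.
- Both times significant: 0.05 + 0.05 − (either). At r = 0 this is 0.10 − 0.0975 = 0.0025.
- Holm with no effect at either time: the chance that the smaller p-value is below 0.025. At r = 0 this is 1 − 0.975² = 0.0494.

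| r | Either time | Either, benefit only | Both times | Holm |
|---|---|---|---|---|
| 0 | 9.75% | 4.9% | 0.25% | 4.9% |
| 0.5 | 9.1% | 4.5% | 0.9% | 4.7% |
| 0.8 | 7.8% | 3.9% | 2.2% | 4.0% |
| 0.9 | 7.0% | 3.5% | 3.0% | 3.6% |
| 0.99 | 5.7% | 2.8% | 4.3% | 2.9% |

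The reference for the benefit-only column is 2.5%; for the other columns it is 5%.

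**Check with the planned test.** Mann-Whitney tests were simulated on an assumed 0 to 7 ordinal score, with an assumed 25 or 50 infants per group and 20,000 trials per setting. At least one time was significant in 9.6% of trials at r = 0, 8.9% to 9.0% at 0.5, 7.5% to 8.1% at 0.8, and 6.9% to 7.2% at 0.9. Here r is the correlation between the underlying scores. The normal approximation is adequate.

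**Holm when only one time has no effect.** That time is never tested at a level above 0.05, so its false-positive chance is at most 5%.

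**The case against.** The strongest reply is that the SAP nowhere says either time suffices. If both were required, the error would be below 5% throughout the table. That is correct, and it is why the size is conditional. It does not remove the omission, because the document does not say that both are required either.

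A second reply is that the aim is directional. A false claim of benefit under the either-time rule occurs at most 4.9% of the time, and the two-sided figure also counts results in which the octopus appears to worsen pain. This stands. The excess is over the nominal level: 5% two-sided, or 2.5% in the favourable direction.

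Four stronger readings are tempting, and the document does not support them:

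- *That the error is at least 7%.* That floor appears only if the correlation is stopped at 0.9. With no correlation given, the supportable range is above 5% and up to 9.75%.
- *That there were three NIPS tests.* With three independent tests the error would be 1 − 0.95³ = 14.3%. But the sentence giving NIPS times lists only 0, 2 and 10 minutes and places the scores on a data collection form. The entry made while the lance was under way concerns the observation form, introduced after the vital signs, and nothing says that it held NIPS. The ambiguity deserves a clarifying sentence, not a larger error estimate.
- *That crying and vital signs multiply the pain claim further.* Nothing says that they support it.
- *That a time was picked on the results.* The dates and tense show that this text cannot prove prior choice. They do not show that a choice was made afterwards. An earlier plan may exist that is not in this document.

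**Conclusion.** The point holds for this document. One pain objective is tested at two post-lance times, each at an unadjusted 5%, with no statement of which result, or how many, decides it. If either time counts and tests are two-sided, the error for the pain claim is above 5% and at most 9.75%; it equals 5% only if the two tests are perfectly correlated. If both times are required, there is no inflation. The omission is certain for this text. Its size rests on the assumed success rule, sidedness and correlation. It should be corrected, because the correction is cheap and the main claim depends on it.

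**What to change.** 1. Define the 2-minute and 10-minute NIPS comparisons as the family for the pain objective, state that tests are two-sided, and apply Holm: the smaller p-value against 0.025 and, only if that passes, the larger against 0.05. Claim an effect only at the time or times that pass. No time has to be chosen after data were seen.
2. Use a single primary NIPS time at 5% only if a plan dated before the data fixed it, and cite that plan. A primary named now could be chosen on the results, which would bring back the either-time error.
3. Present crying and vital signs as secondary, not as support for the pain claim.
4. Reconcile the two Intervention statements on assessment times and say whether NIPS was also scored while the lance was under way. If it was, add that time to the family; the Holm thresholds become 0.05/3 = 0.0167, then 0.025, then 0.05.

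The cost is wording in the SAP and the report, with no new data or staff. The downside is the stricter threshold for the smaller NIPS p-value: two p-values of 0.04, for instance, would each pass an unadjusted 5% test but would not pass Holm.
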